6.5.1.3 Statistical Methods

All statistical analyses for HAI (or MN) titers will be performed on the logarithmically transformed (base 10) values. Individual HAI titers below the detection limit (<10) will be set to half of that limit (5). Individual MN titers below the LLOQ, will be set to half of that limit ($1/2 * \text{LLOQ}$).

Co-primary immunogenicity endpoints of GMT and SCR for each virus strain contained in the vaccine will be assessed in subjects 6 Months through 47 Months of Age overall.

Statistical Analysis Plan

Sponsor Name: Seqirus
Sponsor Protocol ID: V130_10

Primary analysis will be performed in subjects 6 Months through 47 Months of Age for the Per-Protocol Set. The difference in SCRs will be presented with exact 95% CIs. Each of the four strains will be analyzed separately.

For immunogenicity data, the immunogenicity analysis will comprise a complete case analysis only, without introducing any bias. Imputation methods will not be used.

To determine the GMT ratio (adjusted analysis) a general linear model (GLM) will be fitted on log transformed (base ten) post-vaccination HAI (or MN) titer as the outcome variable and terms for covariates: vaccine treatment, pre-vaccination HAI (or MN) titer, age stratum, gender, vaccination history, age-by-vaccine interaction and study site. Potential covariate interaction effects will also be examined in the fit of the GLM. From the model, an adjusted difference in least square means (on the log scale) will be produced with 95% confidence limits. The estimated difference and the confidence limits will be back transformed to obtain an *adjusted GMT ratio* with 95% confidence limits. Each of the four strains will be analyzed separately. The adjusted GMT ratio will be the result for which the non-inferiority assessment of the HAI (or MN) GMT co-primary endpoint will be based on.

The statistical models might be reduced in case they fail to converge.

The complete set of covariates that will be used in the model to calculate the adjusted GMT ratio will include treatment group (2 treatments), pre-vaccination GMT titer (value), age strata (2 categories, 6 through 23 months or 24 through 47 months), gender (male or female), influenza vaccination received prior year (Yes or No), and investigator site (site identifier).

The GLM specification is:

Adjusted Analysis GMT Model: Log-transformed Post-vaccination HAI (or MN) Titer = Vaccine + Age Strata + Gender + Vaccination History [y/n] + Log-transformed Pre-vaccination HAI (or MN) Titer + Site + Age Strata*Vaccine.

For any strain, the interaction term Age Strata*Vaccine will be removed from the fit of the model if it is assessed to be not significant. For all immunogenicity subgroup analysis, the interaction term will be removed in the fit of the model.

The measure of the unadjusted GMT ratio based on post-vaccination GMTs only will also be presented.

Binary data (i.e., percentages of subjects with seroconversion and with titer $\geq 1:40$) will be summarized for each group using unadjusted estimates and will be reported together with two-sided exact 95% CIs. No multiplicity adjustment to the CI levels will be implemented.

If all 8 co-primary endpoints result in a conclusion of non-inferiority, then overall non-inferiority of Seqirus QIVc compared to the US-licensed comparator QIV will be concluded.

Handling of Missing Values for Immunogenicity Data

For immunogenicity data, it may be reasonable to consider missing immunogenicity values as missing completely at random (MCAR), i.e., not informative. Therefore, the immunogenicity and key secondary analyses will comprise a complete case analysis only, without introducing any bias. Imputation methods will not be used.

Sensitivity Analyses for Handling of Missing Immunogenicity Data

To verify the robustness of the primary analysis results, an exploratory analysis may be performed, in which missing titers were imputed using *multiple imputation*. The evaluation of the robustness of the primary analysis results will be based on a pattern mixture model and a 'tipping analyses' approach using multiple imputation methods.

This sensitivity analysis, if conducted, will be based on the per-protocol analysis set and will serve to evaluate the robustness of the non-inferiority conclusions. Appendix C specifies the details of the exploratory sensitivity analysis.

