2.2 Overall Study Design

This multicenter, phase 3 clinical study evaluates the immunogenicity and safety of a cell-based Quadrivalent subunit influenza virus-vaccine (QIVc) compared to US-licensed QIV in children 6 months through 47 months of age. Study features an observer blind, comparator-controlled design and 2:1 randomization between QIVc and US-licensed QIV.

Subjects who meet the eligibility criteria will be enrolled into the study and randomized to one of the two treatment groups using a 2:1 allocation ratio to receive either Seqirus QIVc or US-licensed QIV.

The study has a treatment period and a follow-up period.

Subjects with a previous influenza vaccination history:

- The treatment period begins at the time of vaccination and ends 28 days after vaccination and will consist of 2 clinical visits and one reminder call to complete the Subject Diary Card.
- The follow up period begins 28 days after vaccination and ends at the time of study completion visit.

Subjects without or unknown previous influenza vaccination history:

- The treatment period begins at the time of first vaccination and ends 28 days after the second vaccination and will consist of 3 clinical visits and two reminder calls to complete the Subject diary card, one after each vaccination.
- The follow-up period begins 28 days after second vaccination and ends at the time of study completion visit.

All subjects, irrespective of previous influenza vaccination history, will receive 1 safety assessment call 90 days after last vaccination during the follow up period and the follow-up period will conclude with a study completion visit (call).

Currently available influenza vaccines are not licensed below age of 6 months, and protocol will exclude any subjects who have received influenza vaccine in the past 6 months. Therefore, all eligible subjects below 12 months of age will be considered as not previously influenza vaccinated for enrolment in the study.

The timing and frequency of the study visits are described in Schedule of Assessments ([Appendix A](#)).

The treatment arms of Study Vaccine comprise:

Study treatment:

Seqirus' Quadrivalent (QIVc): Flucelvax Quadrivalent

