2.3 Sample Size and Power

Seqirus QIVc will be tested against comparator, i.e. US-licensed comparator QIV. The treatment randomization ratio is 2:1 (Seqirus QIVc: Comparator QIV).

This study is designed to achieve at least 90% power to demonstrate noninferiority for all of the 8 endpoints: seroconversion rates for 4 strains and Geometric Mean Titers (GMTs) for 4 strains using a one-sided alpha of 0.025 for each comparison. No alpha adjustment for multiple endpoints will be made. For comparisons of Seroconversion rate (SCR) a noninferiority margin of 10% (Comparator QIV-Seqirus QIVc) will be employed. It is assumed that the SCRs for A/H1N1, B strains and A/H3N2 based on Cell-based Trivalent Influenza Vaccine (TIVc) are 81%, 69% and 85% respectively. These estimates are based on the estimated SCR rates of historical data, namely from study *V58P16*.

It is also assumed that the expected difference between antibody titers (QIV minus QIVc) is consistent with the SCR differences reported as per *V58P16*, namely 7% for A/H1N1 and 5% for A/H3N2 (based on the MN assay).

It is assumed that there is no difference between Seqirus QIVc and the comparator QIV for the B/strain.

For comparison of GMT ratio, a noninferiority margin of 1.5 (Comparator QIV/ Seqirus QIVc, equivalent to a difference on the log scale of 0.405465108) will be employed for the assessment for the A/H1N1, A/H3N2 and B strains. It is assumed that the GMT ratios for A/H1N1, A/H3N2 and B strains for QIVc are 1.49 for the A/H1N1, 1.00 for the A/H3N2 (based on the MN assay) and 0.84 for the B-strains. These GMT ratio estimates are consistent to those observed from protocol *V58P16*. It is assumed that the standard deviation of $\log_e(\text{titer})$ is 1.3 across all strains.

Under these assumptions and with n evaluable = 1450 in the Seqirus QIVc group and 725 in the Comparator QIV the power for 4 GMT ratio endpoints is 94.90% and the power for 4 SCR endpoints is 99.40%. The overall global power of the 8 endpoints is then $94.9\% \times 99.4\% = 94.33\%$.

This provides a total N evaluable = 2175. Allowing for a 10% drop-out, 2418 subjects will be recruited for immunogenicity assessment. Approximately 84 additional subjects between 24 through 47 months of age will be enrolled to study CMI

Statistical Analysis Plan

Sponsor Name: Seqirus
Sponsor Protocol ID: V130_10

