6.4 Demographics and Other Baseline Characteristics

All baseline and demographic characteristics will be summarized by vaccine group, age strata, and overall on the FAS population. This will include age (months), gender, race, ethnicity, weight, height, BMI, pre-vaccination temperature, medical history, and previous vaccination status on the FAS population.

Derived variables:

Body Mass Index will be calculated according the following formula:

Body Mass Index (kg/m²): Weight (kg) / Height² (m²)

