6.5.4 Subgroup Analysis

The immunogenicity analyses will be performed by stratifying for the following subgroups:

- Subjects with pre-vaccination HAI titer <1:10 and pre-vaccination HAI titer \geq 1:10.
- Subjects with pre-vaccination MN titer <LLOQ and pre-vaccination MN titer \geq LLOQ.
- Subjects with and without recent seasonal influenza vaccine (defined as influenza vaccine within the past 12 months).
- Subjects "previously influenza vaccinated" and "not-previously influenza vaccinated".
- Subjects aged "6 through 23 months" and "24 through 47 months".
- Subjects by gender.
- Subjects by race.
- Subjects by ethnicity.

The safety analyses will be performed by stratifying for the following subgroups:

- Subjects "previously influenza vaccinated" and "not-previously influenza vaccinated".
- Subjects with and without recent seasonal influenza vaccine (defined as influenza vaccine within the past 12 months).
- Subjects aged "6 through 23 months" and "24 through 47 months".
- Subjects by gender.
- Subjects by race.
- Subjects by time interval as below:
 - Day 1 to Day 29, Day 29 to Day 181 in "previously vaccinated" subjects
 - Day 1 to Day 57, Day 57 to Day 209 in "not previously vaccinated" subjects.

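### The primary GMT model could use age in months and a baseline serostatus term at almost no cost; the four GMT co-primary intervals may be wider than they need be

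*SAP*

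**What the plan says.** SAP 6.5.1.3 fits one general linear model per strain to the log post-vaccination titer. The adjusted GMT ratio from it is the quantity compared with 1.5. The covariate list, which the SAP presents as complete, gives baseline and age as "pre-vaccination GMT titer (value), age strata (2 categories, 6 through 23 months or 24 through 47 months". The other terms are treatment, gender, influenza vaccination in the prior year (yes/no) and site. The printed formula ends "Log-transformed Pre-vaccination HAI (or MN) Titer + Site + Age Strata*Vaccine", and the interaction is dropped where it is not significant. HAI titers below 10 become 5, and MN titers below the LLOQ become half the LLOQ. Protocol 8.4.2.3.3 prints the same formula.

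The finer information is already held:
- Date of birth is collected at screening (protocol 5.1.2). SAP 6.4 says of the baseline summaries: "This will include age (months), gender, race, ethnicity, weight, height, BMI".
- The baseline split at 1:10 is a planned subgroup in SAP 6.5.4: "Subjects with pre-vaccination HAI titer <1:10 and pre-vaccination HAI titer" at or above 1:10.

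On sample size, SAP 2.3 states: "This study is designed to achieve at least 90% power to demonstrate noninferiority for all of the 8 endpoints", "using a one-sided alpha of 0.025 for each comparison". It takes 1450 and 725 evaluable children, an SD of log titer of 1.3, and a B-strain GMT ratio (QIVc over QIV) of 0.84.

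**The concern.** The model gives a child of 6 months and one of 23 months the same age effect, and likewise children of 24 and 47 months. The documents suggest why age inside a stratum could matter. SAP 2.2 says "all eligible subjects below 12 months of age will be considered as not previously influenza vaccinated", whereas children of 12 to 23 months in the same stratum may have been vaccinated before. The comparator volume also changes at 36 months, inside the older stratum, although a linear age term would pick up only part of any effect of that.

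The baseline term is similar. All children below 1:10 sit at a single value, and one straight line must describe both the step from seronegative to seropositive and the slope among seropositive children.

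Variance that these features explain, and the planned terms do not, stays in the residual and widens the intervals held against 1.5. It would matter most for the two B strains, which have the lowest planned GMT power (97.42% each), since all eight endpoints must pass.

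**Working it through.** **1. Reproduce the stated power.** Inputs from SAP 2.3: n = 1450 and 725; SD = 1.3 on the natural-log scale; margin ln 1.5 = 0.4055; B-strain ratio 0.84, so ln(1/0.84) = 0.1744; one-sided alpha 0.025.

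- SE = 1.3 × √(1/1450 + 1/725) = 0.0591
- Distance to the margin = 0.4055 − 0.1744 = 0.2311
- Power per B strain = Φ(0.2311/0.0591 − 1.96) = Φ(1.95) = 97.43% (stated 97.42%)
- A/H1N1 and A/H3N2 are each about 100%, so GMT power = 0.9743² = 94.9% (stated 94.90%)

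This calculation takes no credit for covariates.

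**2. What a variance cut would buy if 1.3 were the residual SD.** Multiply the SD by √(1 − r), where r is the extra share of residual variance explained.

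| r | change in log-scale CI width | power per B strain | both B strains |
|---|---|---|---|
| 0 | 0 | 97.4% | 94.9% |
| 1% | −0.5% | 97.5% | 95.2% |
| 2% | −1.0% | 97.7% | 95.4% |
| 5% | −2.5% | 98.0% | 96.0% |
| 10% | −5.1% | 98.5% | 96.9% |

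A 5% cut is worth 2175/0.95 − 2175 ≈ 114 children.

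**3. The same 5% cut if the planned covariates already explain a share b (assumed).** SD = 1.3 × √((1 − b) × 0.95), against 1.3 × √(1 − b).

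| b | both B strains, planned model | with a further 5% cut | gain (points) |
|---|---|---|---|
| 10% | 96.95% | 97.67% | 0.7 |
| 20% | 98.41% | 98.84% | 0.4 |
| 30% | 99.33% | 99.54% | 0.2 |

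**4. How large r could be.** The documents give no age slope within stratum and no serostatus step, so these are assumptions.

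- *Age, by hand.* Take age uniform over 6 to under 48 months, with a linear effect. The younger stratum holds p = 18/42 of the children. The 24-month split captures 3p(1 − p) = 73% of the age-related variance. The within-stratum age variance left is (18/42) × 18²/12 + (24/42) × 24²/12 = 39. A 2-fold rise over 24 months is a slope of ln 2/24 = 0.0289, leaving 0.0289² × 39 = 0.033, or 1.9% of 1.3² = 1.69. A 1.5-fold rise leaves 0.7%. A smaller residual variance raises these shares.
- *Both terms, by simulation.* With vaccination history and 40 sites in the model, assumed 1.5- to 2-fold effects cut the variance of the vaccine term by roughly 1 to 7%. When neither term is prognostic the variance rises by about 0.1%.
- *Wider grid.* Over 45 scenarios (30 to 85% seronegative, serostatus step 0 to 1.5 ln units, age effect 0 to 0.4 ln units per SD of age) CI width changed by +0.1% to −15.7%. Most scenarios lay between −0.3% and −5%; the extreme needs a very large step and a strong age effect together.

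**The case against.** The strongest reply is that this is a preference about functional form. Adjusting for the stratification factor and log baseline titer is a sound prespecified model, with no bias and no type I error problem. Four parts of the reply have weight.

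- *The effect is not shown.* A reader might infer that the four intervals are wider than they need be. The documents do not support that, because neither gives a within-stratum age slope or a step at 1:10. This part stands in full.
- *The power gain has a soft starting point.* A reader might take 94.9% to 96.0% as the benefit. SAP 2.3 gives 1.3 as the SD of log titer, not as the residual SD of the planned model. If the planned covariates explain anything, power is already higher and the gain smaller (step 3). This stands too.
- *Vaccination history is already in the model.* It covers part of the argument about infants. In a check where age acted only through vaccination history, age in months added nothing (variance +0.04%). This limits the age term but does not exclude an independent effect. The covariate records vaccination in the prior year, whereas the protocol's List of Definitions requires at least two earlier doses for a child to count as previously vaccinated, so it need not absorb all priming.
- *Serostatus is not hidden.* Children below 1:10 sit at their own value, so the slope takes up part of any step. Being a subgroup does not make a variable a needed covariate: race and ethnicity are subgroups and are not in the model. This is fair, but a single line still cannot fit both a step and a slope.

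The planned examination of covariate interactions does not answer the point, because it does not address the form of the age or baseline main effects.

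**Conclusion.** The point holds as a nearly free efficiency improvement. The intervals may be wider than necessary, by an amount that the documents do not allow anyone to fix. A variance cut of 1 to 7% corresponds to 0.5 to 3.6% in log-scale width (1 − √0.99 and 1 − √0.93). For a 5% cut, the gain in joint B-strain GMT power is at most 1.1 points, and 0.2 to 0.7 points if the planned covariates explain 30% to 10% of variance. If neither term is prognostic there is no gain.

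A reader might also infer that the trial is underpowered or the model wrong. Neither follows: the stated GMT power reproduces, and the stated overall power of 94.33% exceeds the 90% target. The case for acting is the asymmetry: a possible gain on the binding GMT endpoints against a cost of about 0.1% of variance.

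**What to change.** In the model of SAP 6.5.1.3, for all four strains and fixed before unblinding:

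- add age in months at first vaccination as a continuous term;
- add an indicator for a pre-vaccination titer below 1:10 (MN: below the LLOQ), specific to the strain and assay analysed;
- keep Age Strata, the log pre-vaccination titer and the other planned terms.

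The cost is two degrees of freedom per model in about 2175 children, and no new data. Both terms are measured before vaccination and the model is linear, so the margin and the target GMT ratio are unchanged. It is not only an SAP edit: protocol 8.4.2.3.3 prints the same formula, so either that text is aligned or the additions are recorded in SAP section 7 as a change in planned analysis. They should not be added after unblinding, when they would look data-driven.

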Not previously influenza vaccinated subject: A subject that has not received 2 or more doses of influenza vaccine prior to the current influenza season, or who does not know the influenza vaccination history.

Previously influenza vaccinated subject: A subject with a known history of at least 2 influenza doses prior to the current influenza season.

Qualified healthcare professional: Any licensed health care professional who is permitted by institutional policy to perform clinical interventions and assessments such as physical examinations, is trained on the study procedure(s) and who is identified within the site signature and delegation log.

Seroconversion Rate (SCR) based on the HAI assay: Seroconversion rate (SCR) defined as the percentage of subjects with either a prevaccination hemagglutinin inhibition (HAI) titer $<1:10$ and a postvaccination HAI titer $\geq 1:40$, or a prevaccination HAI titer $\geq 1:10$ and a ≥ 4 -fold increase in post vaccination HAI titer.

Seroconversion rates (SCRs) based on the Microneutralization (MN) Assay: SCR is the percentage of subjects with either a prevaccination MN titer $<1:10$ (LLOQ) and a postvaccination MN titer $\geq 1:40$ (4*LLOQ), or a prevaccination MN titer $\geq 1:10$ (LLOQ) and a ≥ 4 -fold increase in postvaccination MN titer.

Solicited adverse events: Either solicited local adverse reactions or solicited systemic adverse reactions.

Trained healthcare professional: Any health care professional who is permitted by institutional policy, trained to perform delegated tasks, is trained on the study procedure(s) and who is identified within the site signature and delegation log.

Treatment period: Per protocol treatment period begins at the time of vaccination and ends 28 days after last vaccination, which is visit 2 for previously influenza vaccinated subjects and at visit 3 for not-previously influenza vaccinated subjects.

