Subjects will provide a serological specimen via a blood draw before vaccination on Day 1 and 28 days after last vaccination. Previously vaccinated subjects will provide a serological specimen on Day 1 and Day 29 (vaccination on Day 1), while not previously vaccinated subjects will provide a serological specimen on Day 1 and Day 57 (vaccination at Day 1 and Day 29). The serological specimen on the day of vaccination will be obtained before vaccination. For the majority of subjects (approximately 2418), immunogenicity will be measured by HAI and MN assays from the serological specimen. In a small group of approximately 84 subjects, evaluation of CMI response will be performed instead of the immunogenicity evaluation.

Currently available influenza vaccines are not licensed below the age of 6 months. This protocol will exclude any subjects who have received influenza vaccine in the past 6 months. Therefore, all eligible subjects below 12 months of age will be considered as not previously vaccinated against influenza for study enrollment.

The final analysis of the primary and secondary immunogenicity endpoints will be conducted on cleaned and locked data once all subjects have completed all immunogenicity assessments (end of treatment period, i.e. up to 28 days following the last vaccination dose). At this time, the analysis of all solicited adverse events and of unsolicited adverse events reported during the treatment period will also be conducted. These results will be used to prepare a Clinical Study Report (CSR) with treatment period data. No individual unblinded listings will be generated at this stage. A final CSR will present all clinical study data collected up to 180 days following the last vaccination dose, including safety data collected during the follow up period.

Details of the study procedures and assessments are provided in [Section 5, Study Procedures](#) and [Section 7, Assessments](#), respectively.

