8.4.2.3.3 Statistical Methods

All statistical analyses for HAI (or MN) titers will be performed on the logarithmically transformed (base 10) values. Individual HAI titers below the detection limit (<10) will be set to half of that limit (5). Individual MN titers below the lower limit of quantification (LLOQ), will be set to half of that limit (1/2* LLOQ).

Co-primary immunogenicity endpoints of GMT and SCR for each virus strain contained in the vaccine will be assessed in subjects 6 Months through 47 Months of Age overall.

Primary analysis will be performed in subjects 6 Months through 47 Months of Age for the Per-Protocol Set. The difference in SCRs will be presented with exact 95% (CIs). Each of the four strains will be analyzed separately.

To determine the GMT ratio (adjusted analysis) a general linear model (GLM) will be fitted on log transformed (base ten) postvaccination HAI (or MN) titers as the outcome variable and terms for covariates: vaccine treatment, prevaccination HAI (or MN) titer, age stratum, gender, vaccination history, age-by-vaccine interaction and study site. The complete set of covariates that may be used in the model to calculate the adjusted GMT will be specified in the SAP.

Potential covariate interaction effects will also be examined in the fit of the GLM. From the model, an adjusted difference in least square means (on the log scale) will be produced with 95% confidence limits. The estimated difference and the confidence limits will be back transformed to obtain an *adjusted GMT ratio* with 95% confidence limits. Each of the four strains will be analyzed separately. The adjusted GMT ratio will be the result for which the noninferiority assessment of the HAI (or MN) GMT co-primary endpoint will be based on.

The statistical models might be reduced in case they fail to converge. Further details will be provided in the Statistical Analysis Plan.

The complete set of covariates that may be used in the model to calculate the adjusted GMT ratio will include treatment group (2 treatments), age sub-group, gender (male or female), influenza vaccination received prior year (Y or N), prevaccination mean GMT titer (value) and investigator site (site identifier)

The GLM specification is:

*Adjusted Analysis GMT Model: Log-transformed Postvaccination HAI (or MN) Titer = Vaccine + Age Strata + Gender + Vaccination History [y/n] + Log-transformed Prevaccination HAI (or MN) Titer + Site + Age Strata*Vaccine.*

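### The primary GMT model's vaccination-history term is defined only as prior-year vaccination; adding the screening status that fixes one versus two doses would remove an ambiguity and gain a little precision at almost no cost

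*SAP*

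**What the plan says.** SAP 6.5.1.3 describes the covariates of the primary GMT model three times.

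- The opening text names vaccination history without defining it.
- A fuller list begins "The complete set of covariates that will be used in the model to calculate the adjusted GMT ratio will include treatment group (2 treatments". Its only vaccination item is "influenza vaccination received prior year (Yes or No".
- The equation contains "Vaccine + Age Strata + Gender + Vaccination History [y/n" as one binary term, again undefined.

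Protocol 8.4.2.3.3 has the same structure. Its list gives "influenza vaccination received prior year (Y or N", though it says that these covariates may be used where the SAP says that they will be.

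The trial's own classification is a different variable. The protocol's List of Definitions describes a previously vaccinated child as "A subject with a known history of at least 2 influenza doses prior to the current influenza season" and the opposite as "A subject that has not received 2 or more doses of influenza vaccine prior to the current influenza season", or one whose history is unknown. This status sets the regimen. Protocol 3.1 states that "not previously vaccinated subjects will provide a serological specimen on Day 1 and Day 57 (vaccination at Day 1 and Day 29", while previously vaccinated children have one dose and a Day 29 sample. The status is recorded at screening (protocol 5.1.2).

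SAP 6.5.4 lists vaccination within the past 12 months and previously/not previously vaccinated as two separate subgroup factors. Randomization is stratified by age group only (SAP 2.2).

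**The concern.** Prior-year vaccination and dose status can disagree in eligible children. A child with a single lifetime dose, given last season, is a prior-year Yes but not previously vaccinated, and has two study doses. A child with two doses in earlier seasons and none last year is a prior-year No but previously vaccinated, and has one. The exclusion for recent influenza vaccination reaches back only 6 months (protocol 4.2), so both can enroll. Age stratum does not stand in for status either. Every child under 12 months is not previously vaccinated (protocol 3.1), but older children can have either status.

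If the listed covariate is the one fitted, each of its levels mixes one-dose and two-dose children. Any titer difference between them that the other covariates do not capture stays in the residual and widens the interval compared with 1.5. This bears most on the B-strain GMT ratios, which have the lowest power in SAP Table 2.3-1.

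There is also a specification problem. Two programmers reading the same section could fit different primary models, and prior year is not defined in the model section (last season, or the 12 months of SAP 6.5.4).

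**Working it through.** **Inputs from the documents** (SAP 2.3 and Table 2.3-1; protocol 8.5): 1450 and 725 evaluable children, SD of log_e titer 1.3 (variance 1.69), margin 1.5, assumed B-strain GMT ratio 0.84 (QIVc/QIV), one-sided alpha 0.025.

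**Step 1: reproduce the plan's figures.**

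- SE = 1.3 × √(1/1450 + 1/725) = 0.0591.
- Distance to the margin = ln 1.5 − ln(1/0.84) = 0.4055 − 0.1744 = 0.2311.
- Power per B strain = Φ(0.2311/0.0591 − 1.96) = 97.43% (stated 97.42%).
- The A-strain GMT powers are about 100%, so the four GMT endpoints have 0.9743² = 94.9% (stated 94.90%).
- A normal approximation with unpooled variance, taking the 7% and 5% A-strain differences in favor of QIVc, gives 99.48% for the four seroconversion endpoints (stated 99.40%).
- All eight together: 94.44% (stated 94.33%).

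These figures use an unadjusted SD of 1.3 and no covariates, so the choice of covariate cannot make them wrong.

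**Step 2: the gain from adding status.** Let p be the share previously vaccinated, d the log_e titer difference between status groups that remains after the other covariates, and R² the extent to which those covariates already predict status.

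- Proportional fall in residual variance: r = p(1−p)(1−R²)d²/1.69.
- Equivalent extra children: 2175 × r/(1−r).
- Power: repeat step 1 with SD 1.3 × √(1−r).

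The documents give none of p, d or R². They are assumptions here, as is using 1.69 for the residual variance before status is added. I take p = 0.5, which maximizes p(1−p). For R², I assume prior-year vaccination in 85% of previously and 20% of not previously vaccinated children. The prior-year proportion is then 0.525, and R² = (0.25 × 0.65)²/(0.25 × 0.525 × 0.475) = 0.42. Age would raise R² further.

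| d (log_e) | r | Equivalent children | Power per B strain | Power, both B strains |
|---|---|---|---|---|
| 0 | 0 | 0 | 97.4% | 94.9% |
| 0.25 | 0.5% | 12 | 97.5% | 95.1% |
| 0.5 | 2.1% | 47 | 97.7% | 95.4% |
| 1.0 | 8.5% | 203 | 98.3% | 96.7% |

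With closer overlap (prior-year vaccination in 90% versus 10%, R² = 0.64), d = 0.5 to 1.0 gives r = 1.3% to 5.3%, worth 29 to 122 children.

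**Step 3: check on validity.** In 4000 simulated trials per scenario, with p = 0.35, a twofold titer difference and the 85%/20% overlap, the model with prior-year vaccination only was compared with one that also had status.

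| Quantity | Prior-year only | Prior-year and status |
|---|---|---|
| Mean estimate at the margin (true value 0.405) | 0.406 | 0.406 |
| One-sided error at the margin | 2.1% | 2.2% |
| B-strain GMT power | 98.1% | 98.4% |
| Empirical SE | 0.058 | 0.057 |

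The prior-year model exceeds 97.4% because total variance was held at 1.69 and prior-year vaccination already carries part of the status effect.

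**The case against.** The strongest reply is that the omission is not proven. The equation's label matches the term that protocol 5.1.2 uses for dose status, so the intended covariate may be the right one and the prior-year wording a slip. The GLM code in SAP Appendix B would show which variable is fitted, but it is redacted in the public copy, which is no fault of the plan. This stands: the point is that the list, read as written, leaves status out and the section does not settle the matter.

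The other replies are about size. Prior-year vaccination and age overlap with status, and a calculation that ignores this (R² = 0) would give 3.7% to 14.8% for d = 0.5 to 1.0, which is too much. The documents do not say that dose number is a strong predictor of titer. Earlier priming in the one-dose group could offset the second dose in the other, and prevaccination titer is already in the model. A reader might also count sampling day as a second missing predictor. It is not one: both samples are due 28 days after the last dose, so Day 29 versus Day 57 only restates the number of doses. All of this stands and is why the range is modest.

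Dose status is also a planned subgroup (protocol 8.3.6, SAP 6.5.4). That shows results by status but does not sharpen the primary estimate or say what the term means.

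**Conclusion.** The point holds as a low-severity, nearly free improvement. On the only explicit definition, the primary GMT model adjusts for prior-year vaccination and leaves out the baseline status that fixes one or two doses. The label in the equation can be read either way.

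A reader might infer that the noninferiority comparison is biased, that its error rate is inflated, or that the trial is underpowered. The documents support none of these. Treatment is randomized and the model is linear, so omitting a baseline covariate costs precision only, and the simulation agrees. The seroconversion endpoints are unadjusted. The stated 94.33% reproduces without covariates and exceeds the 90% target.

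Under the assumed even split and R² of about 0.42, the gain is about 2% to 8.5% of residual variance for a remaining difference of 0.5 to 1.0 log_e, and under 1% for 0.25. The real gain could lie outside that range. Clearing up the definition is worthwhile at any value.

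**What to change.** Before unblinding, amend SAP 6.5.1.3 and protocol 8.4.2.3.3 as follows.

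- Add previously/not previously vaccinated status to the covariate list and the equation, as recorded at screening. Use planned status, not doses actually received, so that it remains a baseline covariate.
- Keep prior-year vaccination as a separate term with its own name and a definition of prior year, such as the 12-month definition in SAP 6.5.4.
- Give each term the same name in the opening text, the list, the equation and the analysis code.

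Status is already collected and is already a subgroup factor. The cost is a wording change and at most one degree of freedom among about 2175 evaluable children. Sample size, margins and the seroconversion analysis stay as they are.
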